7. STUDY PROCEDURES

7.1 Duration of Participation

The duration of study participation is up to 216 days. It includes the enrollment period up to 14 days, 2 days of treatment, and 180-200 days of follow up for treatment effect and safety.

7.2 Clinical Evaluations

- At the time of Enrollment, patients will be evaluated for inclusion and exclusion criteria. Demographics and current medications will be documented. Medical history will be obtained with particular attention to the recent CDI history (test result, treatment, hospitalization, weight and if any antibiotics used prior to first CDI episode). History will include obtaining information on solicited symptoms such as diarrhea, nausea, vomiting, gas/flatulence, abdominal distension, abdominal cramps/pain, constipation, rectal bleeding, fatigue/malaise, chills/shivering and fever (> 99.9 F) for two-week period prior to enrollment to establish baseline patterns should an adverse event occur in the future.
- Subjects will collect fresh stool samples at home and bring to the EPDL in transportation provided containers with an ice pack within 6 hours of collection if possible or as quickly as

possible before FMT and at follow up days 1(+3), 7(+3), 14(+3), 30(+10), 60(+10) and 90(+10) and any unscheduled visit up to 60 days after FMT treatment (excluding weekends and holidays). Subject may collect pre-treatment stool on any day after enrollment and before bowel prep on day -1, and can bring stool sample on treatment Day 1 clinic visit. Stool samples collected from subjects until 60-70 days post FMT or at unscheduled visit up to 60-70 days will be tested for *C. difficile* toxins A/B at EPDL in weekly batches. All the stool samples will be stored at -80°C for future microbiome analysis. If a subject is unable to bring stool sample for any reason (e.g. out of town), subject will be asked to ship the sample by Federal Express as expeditiously as possible. A FedEx shipping label, ice pack, Styrofoam container with shipping box and instructions will be provided to the subject to ship stool samples if they are not able to hand deliver the stools to the EPDL. The EPDL will be closed on weekends and holidays. If the follow-up day falls on Friday, Saturday or Sunday, subjects can ship the sample on Thursday or the following Monday. Stool samples that are received out of window are not a protocol deviation; however, missed stool samples are a protocol deviation.

- Subjects will be assessed for vital signs (blood pressure, heart rate, respiration rate, oral temperature, weight) at the day 1 of treatment clinic visit.
- Women of childbearing potential will undergo urine pregnancy testing (Qualitative HCG) to confirm absence of pregnancy at the day 1 of treatment clinic visit prior to administration of study drug.
- A diary completed by subject will be collected before FMT and on follow up days 7(+3), 14(+3) 30(+10), 60(+10), 90(+10) and 180(+20) days after FMT treatment. Subjects may submit diaries with stool samples at the University of Texas School of Public Health, or may fax, email, or mail to the study site. For diary copies received in email or fax, an attempt will be made to obtain the originals from subjects to be taken to the study site subsequently. Diaries serve as tools for subjects to record daily bowel movements and weekly weight. Subjects will be recommended to measure weight at home each Sunday morning before eating and record on follow up diaries providing they have a scale or balance. If they do not have the means to measure their weight this is not a protocol deviation. Additionally, the pre-treatment diary will include daily record of solicited symptoms from day of enrollment until a day before treatment Day 1 (prior to bowel prep) to establish baseline patterns should an adverse event occur in the future. Solicited symptoms include diarrhea, nausea, vomiting, gas/flatulence, abdominal distension, abdominal cramps/pain, constipation, rectal bleeding,

fatigue/malaise, chills/shivering and fever (>99.9 F). The diaries on follow up days 7 and 180 will include a brief survey to assess subject-reported experience of FMT treatment. Diaries that are received out of the window or missed diaries are not a protocol deviation.

Study assessments and procedures will include the following:

- Enrollment visit will occur on day -14 to -1 during which the informed consent will be obtained; inclusion and exclusion criteria will be reviewed; demographics, current medications, the medical history, and the CDI history (including information on solicited symptoms for two-week period prior to enrollment) will be reviewed and recorded. Subjects may already be taking or just have been prescribed antibiotics per standard of care to control recurrent CDI symptoms at the time of enrollment. Subjects who have completed antibiotic therapy will receive four days of oral vancomycin or fidaxomicin daily (PI can call in prescription if needed) prior to the 24-96 hours washout period. A stool collection kit along with IRB approved pretreatment prep instructions, pre-treatment diary, stool collection instructions and directions to drop specimen will be provided to subject.
- A stool sample will be collected by subject during enrollment period (prior to bowel prep) and a pre-treatment diary card will be completed by subject. Study personnel can obtain the stool and diary from subject on treatment Day 1 clinic visit. This stool will go to EPDL at the University of Texas School of Public Health.
- Day -4 to -1 before treatment: remind the subject by email or phone call about clinic appointment time, stopping antibiotic/probiotic/ bile-acid sequestrant, pre-treatment preparation and bringing pre-treatment diary and stool. Day -4 to -1(96 to 24 hours) before treatment: the last day of *C. difficile* antibiotics, non-dietary probiotics and bile-acid sequestrants. Subjects continue taking routine prescription medications.
- Day -1 before treatment: subjects follow a clear liquid diet the entire day. In the evening around 6:00pm, subjects (treatment groups 1-3) who were instructed by the study team during the enrollment will ingest bowel prep.

Treatment Visit: Day 1 (Clinic Visit)

- Subjects are recommended to continue clear liquid diet until after treatment for 1 hour.
- Ensure subject in treatment groups 1-3 has taken bowel prep the evening before and 4mg (2 capsules) of loperamide (Imodium) the morning of treatment (If Imodium

is missed, can be taken within 12 hours of FMT treatment). If bowel prep is missed, subject can proceed with FMT and will be recorded as protocol deviation.

- Collect and review the pretreatment diary with subject to determine baseline pattern of solicited symptoms to assess for adverse events.
- Confirm that the C. difficile antibiotic was stopped 24-96 hours before the visit.
- Perform urine pregnancy test on all female subjects of childbearing potential prior to FMT administration.
- Weight and vital signs (blood pressure, heart rate, respiration rate, oral temperature) will be collected pre-treatment.
- Administer Day 1 dose and dispense Day 2 dose.
- Ask subject if experienced any objectionable taste or smell or difficulty swallowing the capsules and general reaction on taking PRIM-DJ2727 capsules.
- Observe the subject for 1 hour after dosing for any adverse events.
- Collect post-treatment vital signs (blood pressure, heart rate, respiration rate, oral temperature).
- Remind subject that Day 2 dose should be taken the next morning on empty stomach with water.
- Remind subject to continue taking routine prescription medications as needed, but antibiotics, non-dietary probiotics and bile-acid sequestrants may not be taken.
- Release subject with IRB approved aftercare instructions, follow-up paper diaries, visit scheduler, safe antibiotics list and specimen request form.

Second Treatment Dosage: Day 2 (Phone Visit)

- Ask that subject has taken the Day 2 dose.
- Ask for any adverse events since Day 1 assessment.
- Remind subject to follow the aftercare instructions provided on Day 1.
- Remind subject to continue taking routine prescription medications as needed, but antibiotics, probiotics and bile-acid sequestrants may not be taken.
- Remind subject to completely fill the diaries, and submit diaries and stools at follow-up visits according to schedule and instructions provided by study personnel.
- A form letter to subject's physician about FMT completion may be faxed or emailed.

Follow Up and Safety Assessment Period (Phone Visits): Post Treatment Days 1(+3), 7(+3), 14(+3), 30(+10), 60(+10), 90(+10) and 180(+20).

- Assess subject for any adverse events, new illness symptoms, worsening of baseline illnesses including adverse events of special interest (new or worsening autoimmune conditions and metabolic syndrome) and change in medication. Review and assess subject-reported weight data from diaries for AE (>5% change from baseline weight) at days 60 and 180 phone visits.
- Assess subject for solicited symptoms such as diarrhea (passage of ≥ 3 watery stools per 24-hour period for two consecutive days), nausea, vomiting, gas/flatulence, abdominal distension, abdominal cramps/pain, constipation, rectal bleeding, fatigue/malaise, chills/shivering and fever (>99.9 F) for up to 60 days after treatment.
- If CDI recurrence is suspected, subjects should be recommended to contact their physician to perform a stool test for *C. difficile*. EPDL will test scheduled stool specimens and any unscheduled illness stool submitted up to days 60-70 after treatment for *C. difficile* toxins A/B in weekly batches but this should not delay treatment. If the test is positive, they should be treated by their physician. The Principal Investigator will be available for consultation with the attending physician. A form letter may be faxed or emailed to subject's physician about CDI recurrence.
- Subject will be reminded to submit completed diary (except on follow up visit Day 1) and stool sample (except on follow up visit Day 180) and to put stool collection date on provided container (if already submitted, stool collection date should be confirmed).
- Stool samples will be collected at home by the subject and dropped off at the EPDL in the University of Texas School of Public Health in transportation provided containers with ice pack within 6 hours of collection if possible or as quickly as possible (excluding weekends and holidays). Stool sample will not be collected for follow up visit Day 180. If the subject is unable to bring stool sample for any reason (e.g. out of town), subject will be asked to ship the sample by Federal Express as expeditiously as possible. A FedEx shipping label, ice pack, Styrofoam container with shipping box and instructions will be provided to the subject to ship stool sample if they are not able to hand deliver to the EPDL. The EPDL will be closed on weekends and holidays. If the follow-up day falls on Friday, Saturday or Sunday, subjects can ship the sample on Thursday or the following Monday. Stool samples that are received out of window are not a protocol deviation; however, missed stool samples are a protocol deviation.

- Diaries will be collected from subjects recording subject-reported daily bowel movements and weekly weight. The diaries on follow up days 7 and 180 will include a brief survey to assess subject-reported experience of FMT. Diary will not be collected on follow up day 1 after treatment. Subjects may submit diaries with stool samples to the University of Texas School of Public Health, or may fax, email, or mail to the study site. For diary copies received in email or fax, an attempt will be made to obtain the originals from subjects to be taken to the study site subsequently. Diaries that are received out of the window or missed diaries are not a protocol deviation.

Unscheduled Visit (Phone): Subjects who have a suspected episode of CDI within 60-70 days of FMT treatment may submit an unscheduled stool sample to EPDL.

Early Termination Visit (Phone): may occur any time before 180-200 days after FMT treatment.

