 - Remind subject to collect stool sample that will be placed in a transportation container with ice pack and delivered to the EPDL within 6 hours of collection if possible or as quickly as possible (excluding weekends and holidays) to be stored in the EPDL at -80° degrees for possible future testing. Remind subject to put stool collection date on provided container (if already submitted, stool collection date should be confirmed). Stool sample will not be collected for follow up visit Day 180. If hand delivery is not possible, stool sample may be shipped by Federal Express as expeditiously as possible. A FedEx shipping label, ice pack, Styrofoam container with shipping box and instructions will be provided to the subject to ship stool samples if they are not able to hand deliver to the EPDL. The EPDL will be closed on weekends and holidays. If follow-up day falls on Friday, Saturday or Sunday, subjects can collect and ship the sample on Thursday or the following Monday.
 - Remind subject to bring completed diaries with the stool sample, or fax, or email, or mail to the study site. For diary copies received in email or fax, an attempt will be made to obtain the originals from subjects to be taken to the study site subsequently. Diary will not be collected on follow up visit day 1 after treatment.
 - Assess subject for any adverse events, new illness symptoms, worsening of baseline illnesses including adverse events of special interest (new or worsening autoimmune conditions, and metabolic syndrome) and change in medication. Assess and review subject-reported weight data from diaries for AE (>5% change from baseline weight) at days 60 and 180 phone visits.

- Assess subject for solicited symptoms such as diarrhea (passage of ≥ 3 watery stools per 24-hour period for two consecutive days), nausea, vomiting, gas/flatulence, abdominal distension, abdominal cramps/pain, constipation, rectal bleeding, fatigue/malaise, chills/shivering and fever (> 99.9 F) up to 60 days after treatment.

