9.5 Progression of Underlying Conditions and Anticipated events as an Adverse Event

If the symptoms of the primary CDI continue on the study, this is not an AE. If new symptoms develop or worsen after treatment, this is considered an AE.

Anticipated events include diarrhea, nausea, vomiting, gas/flatulence, abdominal distension, abdominal cramps/pain, constipation, rectal bleeding, fatigue/malaise, chills/shivering and fever (> 99.9 F), and may or may not be causally related to the FMT treatment or CDI. These anticipated events will be solicited from subjects at enrollment visit, via pre-treatment diary and at follow-up phone visits. For blinded treatment groups (1-3), mild to moderate diarrhea resulting from taking bowel prep starting a day before treatment and/or mild constipation from taking Imodium on treatment day up to one day after treatment are expected side effects, and should not be recorded as adverse events.

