Flatulence	Symptoms causing no or minimal interference with usual social and functional activities	Symptoms causing greater than minimal interference with usual social and functional activities	NA	NA
Belching (burping)	Symptoms causing no or minimal interference with usual social and functional activities	Symptoms causing greater than minimal interference with usual social and functional activities	NA	NA
Abdominal distension or bloating	Symptoms causing no or minimal interference with usual social and functional activities	Symptoms causing greater than minimal interference with usual social and functional activities	Symptoms causing inability to perform usual social and functional activities	NA

Increased diarrhea	Increase of ≤ 3 stools over baseline per 24- hour period	Increase of 4 – 6 stools over baseline per 24- hour period	Bloody diarrhea if not present at baseline OR increase of ≥ 7 stools over baseline per 24- hour period OR IV fluid replacement indicated if not indicated at baseline	Life-threatening consequences, e.g., hypotensive shock
Abdominal cramping/pain	Discomfort/pain causing no or minimal interference with usual social and functional activities	Discomfort/pain causing greater than minimal interference with usual social and functional activities	Discomfort/pain causing inability to perform usual social and functional activities	Disabling pain causing inability to perform basic self-care OR inpatient hospitalization ≥ 24 hours
Constipation	Occasional or intermittent symptoms, occasional use of stool softeners, laxatives, dietary modifications or enema	Persistent symptoms with regular use of laxatives or enemas indicated	Symptoms causing inability to perform usual social and/or functional activities	Life-threatening consequences, e.g., obstruction, toxic megacolon
Colitis	No symptoms, regardless of pathologic or radiographic evidence of inflammation	Abdominal pain, mucus or blood in the stool	Abdominal pain, fever, change in bowel habits with ileus; peritoneal signs	Life-threatening consequences, e.g., perforation, bleeding, ischemia, necrosis, toxic megacolon

Parameter	Grade 1: Mild	Grade 2: Moderate	Grade 3: Severe	Grade 4: Potentially Life-threatening
Fever	37.7 – 38.6°C (99.9 – 101.5° F)	38.7 – 39.3°C (101.6 – 102.8° F)	39.4 – 40.5°C (102.9 – 104.9° F)	> 40.5°C (104.9° F)

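### After FMT, solicited symptoms other than stool frequency move from a daily diary to phone questioning with nominal gaps of 16 and 30 days after Day 14, and the diarrhea item does not match Table 2

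*Combined protocol and SAP*

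**What the plan says.** Before FMT, Section 7.2 asks for a daily symptom record: "Additionally, the pre-treatment diary will include daily record of solicited symptoms from day of enrollment until a day before treatment Day 1". The diary is reviewed with the subject on treatment Day 1 to fix the baseline pattern. Its symptom list has eleven items: diarrhea, nausea, vomiting, gas, distension, cramps or pain, constipation, rectal bleeding, fatigue, chills and fever.

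After FMT the diary changes. Section 7.2: "Diaries will be collected from subjects recording subject-reported daily bowel movements and weekly weight". The Day 7 and Day 180 diaries add a short survey of the treatment experience. Section 9.5 confirms where symptoms are collected: "These anticipated events will be solicited from subjects at enrollment visit, via pre-treatment diary and at follow-up phone visits". The calls ask about the full list, ending "fatigue/malaise, chills/shivering and fever (>99.9 F) for up to 60 days after treatment".

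The diarrhea item in those calls carries a duration condition. Section 7.2 reads "Assess subject for solicited symptoms such as diarrhea (passage of ≥ 3 watery stools per 24-hour period for two consecutive days), nausea, vomiting", and Section 8.5 repeats it. Section 6 uses the same threshold in the definition of treatment failure. Table 2 grades diarrhea by the rise over baseline in a single 24-hour period; Grade 2, for example, is "Increase of 4 – 6 stools over baseline per 24- hour period".

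Sections 9.1.1 and 9.4 define an adverse event against baseline: a symptom not already in the history or pre-treatment diary, or a pre-existing one that becomes worse or more frequent. Safety is among the primary endpoints in Section 2.

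**The concern.** The baseline and the follow-up of the same symptoms are measured with different instruments, yet each adverse event depends on comparing the two. A daily record shows how often a subject had nausea or cramps before treatment. One phone question covering several weeks does not give a comparable frequency, and it is weakest for mild, short symptoms.

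Grading is affected as well as counting. Table 2 separates nausea lasting up to 24 hours, 24-48 hours and more than 48 hours, and fever by narrow temperature bands. Section 10.2.5 tabulates events by severity, so details lost to recall reach a planned output.

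For diarrhea there is also a conflict of definitions. The solicited item uses the threshold for suspected recurrence, while the grading table has no such condition. Whether a one-day episode is recorded is left to the subject and the caller.

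**Working it through.** The plan states no recall interval, symptom rate or safety power, so there is no figure of its own to reproduce. The gaps follow from the visit schedule.

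**Inputs (Section 7.2, Table 1).** Phone visits on Days 1(+3), 7(+3), 14(+3), 30(+10) and 60(+10). The windows run in one direction only. Symptoms are solicited to Day 60.

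**Formulas.** Nominal gap = next visit day − previous visit day. Longest gap = (next visit day + its window) − previous visit day.

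| Interval | Nominal gap | Longest gap |
|---|---|---|
| Day 1 to 7 | 7 − 1 = 6 | 10 − 1 = 9 |
| Day 7 to 14 | 14 − 7 = 7 | 17 − 7 = 10 |
| Day 14 to 30 | 30 − 14 = 16 | 40 − 14 = 26 |
| Day 30 to 60 | 60 − 30 = 30 | 70 − 30 = 40 |

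One subject cannot have both longest gaps. The 26-day gap needs the Day 30 call on Day 40; the 40-day gap needs it on Day 30. With the Day 14 call on time and the Day 60 call on Day 70, the two gaps total 56 days: 16 + 40 or 26 + 30.

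The two longer intervals cover 60 − 14 = 46 of the 60 solicited days, or 46/60 = 77%. That is a share of calendar time, not of events.

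**What each instrument covers after FMT.**

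| Item | Daily follow-up diary | Phone call |
|---|---|---|
| Stool frequency | Yes | Yes, with the two-day condition in the solicited item |
| The other ten solicited symptoms | No | Yes |
| Diary data the caller is told to review for adverse events | Weight only, at Days 60 and 180 | – |

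**The diarrhea definitions, side by side.** Take, as an invented example, a subject with one stool a day at baseline who passes six watery stools on one day and then returns to one. The rise is 6 − 1 = 5, which is Grade 2 in Table 2. The episode lasts one day, so it does not meet the solicited item in Sections 7.2 and 8.5. It is an adverse event if it is reported under the general question, and it is missed if the subject answers only the specific one.

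**A related inconsistency.** Section 7.2 includes diarrhea in the pre-treatment diary's symptom list; Section 8.1 omits it from the same list.

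**The case against.** There is a substantial case on the other side.

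- **Short diarrhea is not shut out.** The two-day wording belongs to one item in a list of examples. Every call also asks about any adverse event or new symptom, Section 9.1.1 sets no minimum duration, Section 9.6 adds open questions, and Section 10.2.5 tabulates all adverse events with no separate solicited analysis. This stands: a reader might infer that diarrhea counts for safety only if it lasts two days, and the documents do not say so. What remains is two unreconciled definitions.
- **Stool frequency does not rest on recall.** Bowel movements are recorded daily throughout. This also stands, but no rule turns those counts into diarrhea adverse events, and Section 7.2 does not treat a missed diary as a deviation.
- **Early follow-up is close.** There is one hour of clinic observation, a Day 2 call, and no gap over 10 days up to the Day 14 call. Subjects are also told to contact staff with questions about an adverse event (Section 9.2). For events spread evenly over a gap, the average look-back is half of it: 8 and 15 days nominally for the two longer gaps. This confines the weakness to the period after Day 14.
- **The baseline is not purely a daily record.** It includes a two-week recalled history, and because enrollment may fall anywhere from Day −14 to Day −1, some diaries cover few days. This softens the contrast without removing it.
- **Recall may differ in the open group 4.** A reader might add this as a further bias in the comparison with group 3. The documents offer no evidence of it, and a self-completed diary in an open arm would be exposed to the same influence. It is not part of this point.

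**Conclusion.** The point holds in limited form. After FMT, ten of the eleven solicited symptoms have no daily record. From Day 14 to Day 60 they rest on phone questioning with nominal gaps of 16 and 30 days, at most 26 or 40. Because adverse events are judged against a baseline that includes a daily diary, mild and transient symptoms in that period are at risk of under-recording and misgrading. Separately, the solicited diarrhea item and Table 2 use different criteria, and the stool counts that could bridge them are collected without any instruction to use them for adverse events.

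A reader might go further and conclude that the primary safety endpoint is under-counted, or that differences between groups are diluted by some amount. The documents give neither symptom rates nor any measure of how completely recall captures events, so no size can be stated. The collection schedule is the same in all four groups, and Section 10.2.5 plans descriptive tabulation without a powered safety test. The conclusion assumes only that recall over several weeks is less complete for mild, short symptoms than a daily record.

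**What to change.** 1. In Sections 7.2 and 8.5, reconcile the solicited diarrhea wording with Table 2: for safety recording, use the increase in stools over baseline per 24 hours, and keep the two-day definition for suspected recurrence. Have each call to Day 60 review the diary's daily bowel-movement counts against the pre-treatment diary for diarrhea adverse events, and say which pre-treatment days form the baseline count. Align the symptom lists in Sections 7.2 and 8.1. This uses data already collected and costs little beyond the text change and caller time.
2. Carry the existing solicited-symptom checklist onto the follow-up diaries to Day 60, or at least through the longer gaps after Day 14, and review it at each call. Follow-up diaries are already issued and collected at Days 7, 14, 30 and 60.

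The second change needs a revised diary form with IRB approval. It asks modest extra effort of subjects, or of caretakers where Section 4.3 relies on them to record data, and some entries will be missing. The phone questions should therefore stay as a second source.

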6. TREATMENT FAILURES AND RETREATMENT

Treatment failure is defined as the presence of diarrhea (passage of ≥ 3 watery stools per 24-hour period for two consecutive days) and *C. difficile* toxin A/B positive stool within 60 days of FMT treatment and receipt of anti-*C. difficile* antibiotics.

If diarrhea (passage of ≥ 3 watery stools per 24-hour period for two consecutive days) occurs and CDI recurrence is suspected, subjects should inform study team and be recommended to contact their physician to perform a stool test for *C. difficile*. EPDL will test scheduled stool specimens and any unscheduled illness stool submitted up to days 60-70 after treatment for *C. difficile* toxins A/B in weekly batches but this should not delay treatment. If the test is positive, they should be treated by their physician. The Principal Investigator will be available for consultation with the attending physician. Subjects who are determined treatment failures by the investigator will not be followed further for clinical parameters. They will be offered FMT retreatment with maximum dose (200g) from a different donor product if the subject and their physician wish to pursue this treatment. After at least 10-20 days of anti-CDI antibiotics (vancomycin or fidaxomicin) subjects will be eligible for second FMT after 24-96 hour washout. If there is a delay between completing treatment and second FMT, the subject will receive at least four days of vancomycin or fidaxomicin prior to FMT (PI can call in prescription if needed) to complete the treatment 24-96 hours before second FMT. Subjects will be recommended to follow a clear liquid diet the entire day before retreatment clinic visit. Bowel preparation and Imodium will not be required before retreatment. During retreatment clinic visit, vital signs and weight will not be assessed and subjects will be observed for 30 minutes after dosing.

Retreatment Dosage: Day 1 (Clinic Visit)

- Subjects are recommended to continue clear liquid diet until 1 hour after retreatment.

- Perform urine pregnancy test on all female subjects of childbearing potential prior to FMT administration.
- Administer Day 1 dose and dispense Day 2 dose.
- Observe the subject for 30 minutes after dosing.
- Remind subject that Day 2 dose should be taken the next morning on empty stomach with water and release the subject.

Retreatment Dosage: Day 2 (Phone Visit)

- Ask that subject has taken the Day 2 dose.
- Ask for any adverse events since Day 1 assessment.

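### The endpoint needs a toxin A/B positive stool, but the protocol conflicts on whether an illness stool must be sent and has no rule for episodes treated without a toxin result

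*Combined protocol and SAP*

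**What the plan says.** Sections 2 and 9.11 name the efficacy endpoint as prevention of further CDI bouts in the 60 days after FMT. The only operational definition is that of treatment failure, in the Synopsis and section 6. It has three parts, all required. The first is diarrhea: "Treatment failure is defined as the presence of diarrhea (passage of ≥ 3 watery stools per 24-hour period for two consecutive days". The second and third are a *C. difficile* "toxin A/B positive stool within 60 days of FMT treatment and receipt of" anti-*C. difficile* antibiotics.

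When recurrence is suspected, section 6 says subjects should tell the study team and "be recommended to contact their physician to perform a stool test for" *C. difficile*. Sections 7.2, 7.3, 8.1 and 8.5 give the same advice. None names an assay, and none asks for the outside report. If the test is positive, the physician treats.

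The study laboratory (EPDL) runs toxin A/B on scheduled stools and on "any unscheduled illness stool submitted up to days 60-70 after treatment". It does so "in weekly batches but this should not delay treatment".

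On whether the illness stool must be sent, the text differs by place:

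- Section 7.2, Unscheduled Visit: "Subjects who have a suspected episode of CDI within 60-70 days of FMT treatment may submit an unscheduled stool sample to EPDL".
- Section 7.2 (opening bullets) and sections 7.4, 8.1 and 9.12: stool will be collected on the scheduled days and at any unscheduled visit, to Day 60 or to Day 60-70 depending on the section.
- Section 7.2, twice: a missed stool is a protocol deviation.

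Section 6 states that diarrhea with a negative toxin A/B test is not a failure. It says nothing about diarrhea with no toxin test.

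**The concern.** The laboratory part of the primary endpoint may go unmeasured in a subject who has a real recurrence. It then depends on which test an outside physician orders and on whether the subject sends an extra stool, and the protocol gives two answers on whether that stool is required.

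If such episodes drop out of the failure count, efficacy is overstated in every group and absolute differences between doses shrink. If the chance of testing or sending a stool differs in group 4, the only unblinded group, the group 3 versus 4 comparison could be biased in either direction.

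**Working it through.** **1. One episode followed through the text.** A subject has qualifying diarrhea on Day 40, after the Day 30 stool. The physician orders a test that does not report toxin, it is positive, and antibiotics start. No illness stool goes to EPDL. Parts one and three of the definition are met; part two was never measured. Section 6 covers a negative toxin test only. Section 10.2.3 analyses everyone in whom the procedure was begun and gives no missing-outcome rule. On the wording of the definition the subject is not a failure.

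**2. What the scheduled stools can recover.** Toxin-tested stools fall on Days 1, 7, 14, 30 and 60. None is scheduled between Days 14 and 30 or between Days 30 and 60. The Day 60 stool has a +10 day window, so it may be taken as late as Day 70. In the example it would be collected after treatment had started.

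**3. The plan's own power figure.** Section 10.2.2 assumes efficacy of 88%, 80%, 70% and 80% (failure 12%, 20%, 30%, 20% in groups 3, 2, 1, 4), 348 subjects (87 per group) and two-sided alpha 0.05, and states 85% power for the four-group comparison. For a Pearson chi-square test the noncentrality is λ = n × Σ(p − p̄)² / [p̄(1 − p̄)].

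- Four groups: 87 × 0.0163 / (0.205 × 0.795) = 8.70 on 3 df, power 69.5% (simulation 69.8%). The stated 85% is not reproduced. It lies close to group 1 versus 3 alone (84.8%, unpooled) or a three-group trend test (83.9%). That is a separate matter.
- Three dose groups, the first primary analysis in section 10.2.3: 87 × 0.016267 / (0.20667 × 0.79333) = 8.63 on 2 df, power 75.2% (simulation 76.1%). This is the baseline used below.

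**4. Effect of missed recurrences.** Let q be the share of true recurrences with no toxin result that are scored as non-failures. Recorded failure = true failure × (1 − q). The documents give no value for q; 10% to 30% is an assumption. Power is at 87 per group, simulated with 400,000 trials.

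| q | Recorded failure, groups 1/2/3 | Group 1 − 3 | λ | Power, formula | Power, simulated | Trend test, simulated |
|---|---|---|---|---|---|---|
| 0 | 30 / 20 / 12% | 18.0 points | 8.63 | 75.2% | 76.1% | 84.4% |
| 10% | 27 / 18 / 10.8% | 16.2 | 7.57 | 69.2% | 69.7% | 79.4% |
| 20% | 24 / 16 / 9.6% | 14.4 | 6.56 | 62.5% | 62.9% | 73.3% |
| 30% | 21 / 14 / 8.4% | 12.6 | 5.60 | 55.3% | 55.8% | 66.3% |

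At q = 30%, recorded efficacy in groups 1, 2 and 3 would read 79%, 86% and 91.6% in place of 70%, 80% and 88%.

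**5. Unequal loss, groups 3 and 4 (illustration only).** Assume equal true failure of 20%, with 10% missed in group 3 and 40% in group 4. Recorded failure is 20% × 0.9 = 18% and 20% × 0.6 = 12%. At 87 per group, a two-sided 5% test of proportions would favour group 4 falsely in about 20% of trials, against a nominal 2.5% in that direction. With equal true failure of 12% the figure is about 13%. Reversing the loss would favour group 3.

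**The case against.** The strongest reply is that the illness stool is not really optional. Sections 7.2, 7.4, 8.1 and 9.12 say stool will be collected at unscheduled visits, and a missed stool is a deviation. This stands in part: a reader who infers from the Unscheduled Visit sentence alone that collection is optional goes beyond the documents. But nothing requires an unscheduled visit when an episode occurs, and where one sentence is permissive it is unclear that an unsent stool counts as missed. The conflict is the defect.

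Second, a reader might infer that untested recurrences count as cures. The documents do not say so. Section 6 refers to failures determined by the investigator, and section 4.8, read literally, could instead exclude the subject from efficacy for taking any systemic antibiotic. Section 7.3 limits that exclusion to non-*C. difficile* antibiotics, which is the coherent reading because failure itself requires anti-*C. difficile* treatment. Scoring as a non-failure therefore follows from the wording of the definition, but it is not a stated rule.

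Third, the context is toxin testing: entry requires positive toxin tests, EPDL's assay is toxin A/B, and the Principal Investigator is available to the physician. Subjects also have a reason to document failure, since failures are offered retreatment. Phone contacts ask about diarrhea and medication changes. These points should reduce the loss, but none of them produces a toxin result.

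Finally, equal loss leaves risk ratios unchanged (30/12 = 21/8.4 = 2.5), and unequal testing in group 4 is a possibility, not something the documents show. Both points stand.

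**Conclusion.** The point holds as an inconsistency and an unfilled rule in how the primary endpoint is ascertained. Three things are certain from the text: failure needs a toxin A/B positive stool, the protocol disagrees with itself on whether the illness stool must be sent, and nothing says how to score an episode treated without a toxin A/B result.

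The size is not known. The loss of 1.8 to 5.4 points from the 18-point difference, and of about 6 to 20 percentage points of three-group power, depends wholly on the assumed 10% to 30%. It also requires that each missed episode had no outside toxin result, no illness stool and no positive scheduled stool, and was scored as a non-failure. The figures should not be read as a forecast. Section 10.2.6 expects trends only, so the possible bias in the efficacy estimates matters at least as much as the power.

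The change is worth making because it is cheap and affects measurement only.

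**What to change.** 1. In section 7.2 (Unscheduled Visit), change *may submit* to *will submit* for every suspected episode to Day 60. Bring sections 6, 7.3, 7.4, 8.1, 8.5 and 9.12 into line, including the differing 60 and 60-70 day limits. Keep the statement that treatment does not wait; nothing in clinical care changes.
2. Name the EPDL toxin A/B result as the endpoint assay.
3. Collect the report and assay type of every outside *C. difficile* test on the case report form, and state whether an outside toxin A/B result may stand in when no EPDL result exists.
4. Pre-specify in section 10.2 how an episode treated without a toxin A/B result is scored. Add a sensitivity analysis counting it as failure, and tabulate such episodes by group. Reconcile sections 4.8 and 7.3 so that these subjects are not excluded by one and retained by the other.

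The cost is small. Stool kits, shipping and EPDL testing of unscheduled stools are already in the plan. The downside is a few more kits and some missed illness stools logged as deviations.
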